Participants will assess the severity of 7 influenza-associated symptoms (cough, sore throat, headache, nasal congestion, feverishness/chills, muscle/joint pain, and fatigue) on a 4-point scale (0 = no symptoms, 1= mild, 2 = moderate, and 3 = severe) as specified in section 4.5.7. Improvement is defined as: improvement pre-existing symptoms (i.e cough, fatigue, or muscle/join pain that existed prior to influenza) that were worse at baseline and improve at least 1 point from baseline; pre-existing symptoms not worse at baseline that maintain baseline severity; and new symptoms that are alleviated, defined as a symptom score of non (0) or mild (1).

Once all patient's influenza symptoms are alleviated, maintained, or improved (hereafter all will be called 'improvement') as defined above, the endpoint will be reached.

6. **Percentage of patients who experience each influenza-related complication** (hospitalization, death, sinusitis, otitis media, bronchitis, and radiologically-confirmed pneumonia) as an adverse event after the initiation of study treatment symptoms [symptoms [Time Frame: From Day 1 pre-treatment up to Day 30].
7. **Time to Return to Preinfluenza Health Status** [Time Frame: From Day 1 pre-treatment up to Day 30]. Participants will be asked to record their preinfluenza health status on a scale from 0 (worst possible health) to 10 (normal health [for someone same age and condition]), and their health status at baseline and every day after initiation of study treatment on the same scale as specified in section 4.5.7. Return to preinfluenza health status is defined as time from the initiation of the study treatment to the first time when the health status score was equal to or higher than the preinfluenza health status score.
8. **Time to viral clearance**, as assessed by difference in Percentage of Participants Positive by Influenza plaque assay and qPCR at each time-point (in each treatment group) The definition of the time to sustained cessation of infectious virus detection is the time

between the start of treatment and when virus titer remained below the detection limit on all subsequent sampling time points.

9. Measure treatment-emergent variants of neuraminidase and polymerase known to confer antiviral resistance to oseltamivir in each arm by direct next-generation sequencing symptoms [Time Frame: From Day 1 pre-treatment up to Day 30]

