10. Safety and tolerability of Baloxavir in Combination with SOC treatment as assessed by Percentage of Participants with Adverse Events (AEs) [Time Frame: From first dose of study drug to Day 15]

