3. STUDY DESIGN

3.1 DESCRIPTION OF THE STUDY

This is a randomized double-blind placebo-controlled pilot study of the efficacy and safety of baloxavir in combination with oseltamivir (SOC) for the treatment of influenza in allogeneic stem cell transplant patients.

30 SCT recipients with influenza will take part in the study. Participants will be randomly assigned (1:1) to either baloxavir + oseltamivir or baloxavir-matched placebo +oseltamivir. Randomization will be performed by research pharmacy using an interactive web randomizer. Before randomization, patients will be stratified by hospitalization status (yes or no), influenza type A (yes or no).

Patients in the baloxavir combination arm will receive weight-adjusted baloxavir (40 mg for patients weighing <80 kg and 80 mg for those weighing \geq 80 kg) at baseline and at day 4 and day 7. They will also receive oseltamivir 75 mg twice daily for 10 days.

Patients in the baloxavir-matched placebo + oseltamivir arm will receive baloxavir-matched placebo at baseline and at day 4 and day 7 and oseltamivir 75 mg twice daily for 10 days.

Nasopharyngeal swabs will be collected on days 1 (at diagnosis, pre-meds), 2, (optional visit), 4, 7 and 10 for viral quantitation and viral sequencing. Influenza virus polymerase and neuraminidase sequencing will be also performed in all patients. Patients will have follow-up visits day 15 (+/- 2 days) and day 30 (+/- 2 days, EOT). Patients who will not clear the virus by day 10 will perform additional NP swabs at these visits.

Paracetamol (acetaminophen; maximum 3000 mg per day) or NSAIDS can be given for severe discomfort or fever. No other antiviral drugs for the treatment of influenza, will be permitted, except antibiotics for the treatment of suspected bacterial infections.

For the first 10 days, patients will receive a daily call from one member of the study team to review symptoms and severity scale.

To assess the **time to improvement of individual influenza symptoms** (with modification for preexisting symptoms), participants will be given a diary to self-assess the severity of seven influenza-associated symptoms on a four-point scale. To evaluate patient-reported **time to return to pre-illness health status**, patients will also rate **daily the interference of influenza symptoms in daily activities** on a 5-point severity scale.

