5.3.2 ADVERSE EVENT REPORTING PERIOD

The study period during which AEs and SAEs as described in **section J** where the patient has been exposed to Genentech product must be reported. Reporting period begins after informed consent is obtained and initiation of study treatment and ends 30 days following the first administration of study treatment or study discontinuation/termination, whichever is earlier. After this period, investigators should only report SAEs that are attributed to prior study treatment.

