Appendix 1 - Study Flowchart

Day(s)	D1	D2^a	D3	D4	D5	D6	D7	D8	D9	D10	D11 – D14	D15^b	EOS D30^{b,c}	Unsched Visit
On-site study visit	x	(x)		x			x			x		x	x	
Phone Visit			x	x		x	x		x	x				
Screening	x													
Informed consent and assent	x													
Inclusion/Exclusion criteria	x													
Randomization^d	x													
Demographics	x													
Medical history	x													
Concomitant medication monitoring	x			x			x			x		x	x	x
Physical examination^e	x ^e	x		x			x			x		x ^f	x ^f	x ^g
Body weight	x											x ^f		
Vital sign measurements^h	x											x ^f	x ^f	x ^g
Presence or absence of respiratory supportⁱ	x	x		x			x			x		x ^f	x ^f	x ^g
Blood hematology and chemistry^j	x			x ^f			x			x		x ^f	x ^f	x ^g
Blood liver chemistry^k	x			x			x			x		x ^f	x ^f	
Blood for exploratory biomarkers	x	x		x			x			x		x	x	
NP swab^l	x	x		x			x			x		x	x	x ^a
Chest X-ray/CT Scan^m	x													

Day(s)	D1	D2 ^a	D3	D4	D5	D6	D7	D8	D9	D10	D11 – D14	D15 ^b	EOS D30 ^{b,c}	Unsched Visit
On-site study visit	x	(x)		x			x			x		x	x	
Phone Visit		x	x		x	x		x	x					
Pregnancy test ⁿ	x													
Adverse events		x		x			x			x		x	x	x
Patient self assessment ^o	x	x	x	x	x	x	x	x	x	x	x	x	x	x
Xofluza/Placebo ^p	x			x			x							
NAI SOC (Oseltamivir) ^q	x	x	x	x	x	x	x	x	x	x				

CT = computed tomography; D = day; EOS = end of study; Hosp = Hospitalized; NAI = neuraminidase inhibitor; Random = Randomization; RIDT = Rapid Influenza Diagnostic Test; RT-PCR = reverse transcription polymerase chain reaction; SOC = standard-of-care; Unsched = Unscheduled; V = visit; VHP = Voluntary Harmonization Procedure.

- a. Optional visit
- b. A visit window of ± 2 days applicable.
- c. The EOS visit should occur approximately 20 days after the last dose of study drug.
- d. Randomization should occur as soon as possible, after screening and informed consent.
- e. A complete physical examination should be conducted at screening. At post baseline visits and as clinically indicated, limited, symptom directed physical examinations should be performed.
- f. Clinical procedures may be undertaken at investigator's discretion if symptoms and signs persist beyond the treatment period or if viral shedding is detected beyond Day 10.

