- g. Perform assessments at any unscheduled visits based upon clinician's discretion.
- h. During the study treatment period (Day 1/Visit 1 to Day 10), all vital sign measurements (i.e., respiratory rate, pulse rate, peripheral oxygen saturation, systolic and diastolic blood pressures, and body temperature) should be recorded when on-site. For all other visits, the only vital signs measurement taken will be temperature. After day 10 vital sign measurements and specific assessments are to be recorded at the investigators' discretion (e.g., if symptoms and signs persist during follow-up).
- i. Presence or absence and type of respiratory support; oxygen saturation.
- j. See Section X for tests included in laboratory panels.

- k. Liver function test results to be reviewed by the investigator before Xofluza, or its matching placebo, is administered. On Day 1, prior blood results if tests conducted within 24 hours prior to screening. On Day 4 and day 7, blood liver chemistry panel should be reviewed before the patient will receive Xofluza or matching placebo on this study day.
 - l. Nasopharyngeal swabs for RT-PCR: RT-PCR for influenza and covid-19 should be performed at screening.
 - m. If a chest X-ray has not been taken within the 24 hours prior to screening, it will be performed per clinical provider decision. If the SOC is a chest CT scan, this can be used as alternative to the chest X-ray per clinical provider decision.
 - n. All women of childbearing potential will have a pregnancy test at screening (urine or serum).
 - o. Self-assessment of seven influenza-associated symptoms (cough, sore throat, headache, nasal congestion, feverishness or chills, muscle or joint pain, and fatigue) on a four-point scale (with 0 indicating no symptoms, 1 mild symptoms, 2 moderate symptoms, and 3 severe symptoms) twice daily from enrolment (day 1) until day 9 and once daily on days 10–15, and record their results in the patient diary.
 - p. Baloxavir treatment or Baloxavir-matched placebo dosing will occur on Day 1 and Day 4, with a further dose at Day 7
 - q. The SOC NAI (Oseltamivir) will be administered from Day 1 through Day 10.

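### The overall safety endpoint stops at Day 15, although adverse events are collected for 30 days; late events outside the complications list belong to no named endpoint

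*Combined protocol and SAP*

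**What the plan says.** Four places bear on the adverse event window.

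- **Section 2.1, secondary endpoint 10.** Safety and tolerability are measured by the percentage of participants with adverse events, "From first dose of study drug to Day 15". This is the only endpoint for overall safety.
- **Section 5.3.2.** The reporting period for adverse events and serious adverse events "ends 30 days following the first administration of study treatment or study discontinuation/termination, whichever is earlier". Appendix 1 agrees: its adverse event row is marked at Days 2, 4, 7, 10, 15 and 30 and at unscheduled visits.
- **Section 2.1, secondary endpoint 6.** Each of six complications (hospitalization, death, sinusitis, otitis media, bronchitis, radiologically confirmed pneumonia) is counted "as an adverse event after the initiation of study treatment", with "Time Frame: From Day 1 pre-treatment up to Day 30".
- **Statistical Considerations.** Adverse events are summarized as counts and proportions by arm, with Fisher's exact test for exploratory comparison. No time window is stated.

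No section explains the Day 15 limit.

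**The concern.** Two endpoints in the same list treat the same kind of event differently. A pneumonia first diagnosed on Day 20 is an adverse event under endpoint 6 but does not count towards endpoint 10.

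The larger gap concerns events that endpoint 6 does not list. A potential drug-induced liver injury is an adverse event of special interest in Section 5.4.4, and hypersensitivity is the post-marketing signal in Section 1.2.2. If either first occurs on Days 16 to 30 it is collected and reported, but no named endpoint includes it.

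Because the statistical section is silent, whoever programs the adverse event table must choose a window. Day 15 follows the endpoint and Day 30 follows the collection period, and the two can give different percentages. That choice should be written down before unblinding.

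**Working it through.** The plan states no figure to reproduce here, so the check compares windows.

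**Inputs.** Endpoint 10 ends on Day 15 (Section 2.1). Collection ends 30 days after first dose (Section 5.3.2). The Day 15 and Day 30 visits each have a window of ±2 days (Section 3.1, Appendix 1). The last oseltamivir day is Day 10: "The SOC NAI (Oseltamivir) will be administered from Day 1 through Day 10". There are 15 participants per arm (Statistical Considerations).

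**Share of collected days outside the endpoint**, as (end of collection − end of endpoint) / end of collection:

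- Nominal days: (30 − 15)/30 = 50%.
- If 30 days following first dose on Day 1 means Day 31: (31 − 15)/31 = 16/31 = 51.6%.
- Extremes of the visit windows: (28 − 17)/28 = 39% and (32 − 13)/32 = 59%.

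**Share of post-treatment days.** Days 11 to 30 are 20 days. Endpoint 10 covers Days 11 to 15, which is 5, and leaves out 15/20 = 75%.

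**Effect of one participant.** 1/15 = 6.7 percentage points in that arm. The endpoint counts participants, not events, so this applies only to a participant whose first adverse event comes after Day 15. For anyone already counted by Day 15, a late event changes nothing.

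**Illustration of participants missed.** The documents give no timing of adverse events, so this rests on two assumptions: a constant hazard over 30 days, and an assumed proportion p30 with any adverse event by Day 30. Then p15 = 1 − √(1 − p30), and the share missed is 1 − p15/p30.

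| p30 (assumed) | p15 | Of 15: by Day 30 / by Day 15 | Share missed |
|---|---|---|---|
| 30% | 16.3% | 4.5 / 2.5 | 46% |
| 45.2% | 26.0% | 6.8 / 3.9 | 43% |
| 70% | 45.2% | 10.5 / 6.8 | 35% |
| 90% | 68.4% | 13.5 / 10.3 | 24% |

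The 45.2% row borrows the proportion with any adverse event in the baloxavir arm of the FLAGSTONE table (Section 1.3). Its follow-up length is not stated, so it is only an anchor. If adverse events cluster in the treatment period, fewer participants are missed than the table shows.

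**The case against.** The strongest reply is that the windows serve different purposes. Endpoint 10 concerns tolerability of a regimen that ends on Day 10, and Section 3.1 lists safety laboratory tests on Days 1, 7 and 15 only. In Appendix 1, examinations and blood tests at Day 30 are at the investigator's discretion, and Section 3.1 limits the daily calls to the first 10 days. A Day 15 cut therefore fits the period of closer observation. This stands as a reason to keep a Day 15 summary and as a caveat on later data. It does not justify leaving out adverse events that the protocol already collects.

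A second reply is that the statistical section sets no limit, so a Day 30 table is not ruled out. That is true, but nothing plans one, and silence there does not override the explicit Day 15 limit in the endpoint.

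Some stronger readings are tempting and are not supported:

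- **A reader might infer that late deaths go unanalysed.** Death, hospitalization and pneumonia to Day 30 are in endpoint 6, and the hospital recovery scale (Section 4.5.6) records status, including death, to Day 30.
- **A reader might infer that a formal safety comparison is compromised.** The statistical section calls all between-arm comparisons exploratory.
- **A reader might argue that the combination has no human safety data.** Section 1.3 says that no human data on combination therapy are available, but the same section tabulates adverse events in 239 patients on baloxavir plus a standard-of-care neuraminidase inhibitor.
- **A reader might argue from baloxavir's half-life that Day 15, 8 days after the Day 7 dose, is too early.** Section 1.3 calls the half-life prolonged but gives no figure, so this cannot be judged from the documents.

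**Conclusion.** The mismatch is real and limited in reach. Followed as written, the only overall safety endpoint drops participants whose first adverse event falls on Days 16 to 30. Late adverse events outside endpoint 6's six complications have no named endpoint. Collection and safety reporting are unaffected.

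Its size is 15 of 30 collected days on nominal counting, or 39% to 59% across the visit windows. This is a share of calendar days; it would be wrong to read it as half of the events or half of the safety information. For a participant with no adverse event by Day 15, a late one is worth 6.7 points in that arm. How many such participants there would be cannot be derived from the documents. Under the constant-hazard illustration it is about 2 to 4 of 15 per arm, and fewer if events come early.

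**What to change.** 1. Set the time frame of secondary endpoint 10 to the Section 5.3.2 reporting period, 30 days after first dose.
2. State the same window in the Statistical Considerations section, and define the last day once (Day 30 or Day 31) so that endpoints 6 and 10 and Section 5.3.2 agree.
3. Keep first dose to Day 15 as an additional summary, labelled treatment plus 5 days, since dosing ends on Day 10.
4. Report both windows by arm, with the number of participants followed to each, because Section 5.3.2 ends collection early for those who leave the study.

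The cost is a few phrases. Visits, data collection, sample size and power do not change. There is a small downside: the longer window takes in more background events in a sick population, and ascertainment after Day 15 is lighter because Day 30 examinations and laboratory tests are discretionary. Showing both windows lets the reader see this.

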1.2.1 EXPLORATORY EFFICACY OBJECTIVES

1. To evaluate the use of cell-free DNA as surrogate for organ damage and treatment response

The exploratory efficacy endpoint is:

1. Measure change in organ damage and response to treatment by using cell-free DNA as surrogate.

3. STUDY DESIGN

3.1 DESCRIPTION OF THE STUDY

This is a randomized double-blind placebo-controlled pilot study of the efficacy and safety of baloxavir in combination with oseltamivir (SOC) for the treatment of influenza in allogeneic stem cell transplant patients.

30 SCT recipients with influenza will take part in the study. Participants will be randomly assigned (1:1) to either baloxavir + oseltamivir or baloxavir-matched placebo +oseltamivir. Randomization will be performed by research pharmacy using an interactive web randomizer. Before randomization, patients will be stratified by hospitalization status (yes or no), influenza type A (yes or no).

Patients in the baloxavir combination arm will receive weight-adjusted baloxavir (40 mg for patients weighing <80 kg and 80 mg for those weighing \geq 80 kg) at baseline and at day 4 and day 7. They will also receive oseltamivir 75 mg twice daily for 10 days.

Patients in the baloxavir-matched placebo + oseltamivir arm will receive baloxavir-matched placebo at baseline and at day 4 and day 7 and oseltamivir 75 mg twice daily for 10 days.

Nasopharyngeal swabs will be collected on days 1 (at diagnosis, pre-meds), 2, (optional visit), 4, 7 and 10 for viral quantitation and viral sequencing. Influenza virus polymerase and neuraminidase sequencing will be also performed in all patients. Patients will have follow-up visits day 15 (+/- 2 days) and day 30 (+/- 2 days, EOT). Patients who will not clear the virus by day 10 will perform additional NP swabs at these visits.

Paracetamol (acetaminophen; maximum 3000 mg per day) or NSAIDS can be given for severe discomfort or fever. No other antiviral drugs for the treatment of influenza, will be permitted, except antibiotics for the treatment of suspected bacterial infections.

For the first 10 days, patients will receive a daily call from one member of the study team to review symptoms and severity scale.

To assess the **time to improvement of individual influenza symptoms** (with modification for preexisting symptoms), participants will be given a diary to self-assess the severity of seven influenza-associated symptoms on a four-point scale. To evaluate patient-reported **time to return to pre-illness health status**, patients will also rate **daily the interference of influenza symptoms in daily activities** on a 5-point severity scale.

Oral temperature will be measured by the patient (in the outpatient setting) or by the staff for inpatients in the am and pm daily until day 10.

To evaluate **incidence of complications associated with influenza** after the start of study treatment, at each study visit investigators will assess whether each of the complications (sinusitis, otitis, bronchitis, pneumonia) is present or not. If present, the report form shown in section will be completed. For pneumonia, a radiological confirmation will be required.

On days 1, 7 and 15 safety laboratory tests (CBC, blood chemistry with LFTs) will be done.

3.2 END OF STUDY AND LENGTH OF STUDY

The end of this study is defined as the date when the last patient, last visit (LPLV) has occurred, patient has become lost to follow up, patient has withdrawn consent, or patient has completed at least 1 months of follow-up after randomization. The end of the clinical part of the study is expected to occur two months after the last patient is enrolled. After that the study will be open for analysis only. In addition, the Investigator may decide to terminate the study at any time.

The total length of the study, from screening of the first patient to the end of the study, is expected to be approximately 24 months.

3.3 RATIONALE FOR STUDY DESIGN

3.3.1 RATIONALE FOR XOFLUZA DOSE

The dose of Xofluza for this study was selected based on the results of Study 1601T0831 (CAPSTONE-1). This study compared the effects of a single dose of Xofluza (40 mg for patients <80 kg and 80 mg for patients \geq 80 kg administered as 20 mg tablets) with placebo or oseltamivir in otherwise healthy patients with influenza aged \geq 12 to \leq 64 years of age. Study 1601T0831 demonstrated that a single 40 mg/80 mg dose on Day 1 was well tolerated and significantly reduced the time to alleviation of symptoms. This dose and regimen were also effective at reducing viral load. In the Flagstone study, baloxavir dosing at day 0, 4 and optional day 7 was used for treatment of influenza on hospitalized patients. Since SCT recipients are immunocompromised and have severe and prolonged disease we will use the same dose of baloxavir that is used for hospitalized patients in SCT with influenza treated both as outpatients or inpatients.

3.3.2 RATIONALE FOR PATIENT POPULATION

As described above, treatment with Xofluza has been shown to reduce viral load and symptoms in patients with influenza A or B. Therefore, this study was designed to determine if adding baloxavir to oseltamivir will translate into a reduction in viral titer and symptoms.

3.3.3 RATIONALE FOR THE CONTROL GROUP

This is a placebo+oseltamivir -controlled study because oseltamivir is standard of care treatment for influenza in SCT. Since SCT patients usually are unable to clear infection after 5 day-course of oseltamivir, we will use a 10-day course that is the standard of care (SOC) in the Weill Cornell Medicine BMT clinic. Comparison with placebo + oseltamivir will enable the analysis of the effect of combination therapy with baloxavir on influenza viral titers and clearance.

3.3.4 RATIONALE FOR BIOMARKER ASSESSMENTS

Short fragments of cell-free DNA (cfDNA) circulate in blood. These molecules are the circulating debris of the genomes of dead cells, and their importance in diagnostic medicine has been widely established. The value of cfDNA as a quantitative marker of tissue and organ injury was first recognized in solid-organ transplantation, where the level of transplant donor derived cfDNA in the blood is now widely used as a marker of transplant rejection. More recently, several approaches have been developed to quantify the cell-, tissue-, and organ-of-origin of cfDNA and to thereby monitor injury to any cell, tissue or organ types. This is achieved by profiling of cell-, tissue-, or organ-specific epigenetic marks within cfDNA by quantitative molecular measurement technologies such as DNA sequencing. Here, we will test the hypothesis that profiling the cfDNA tissues-of-origin would enable identifying specific tissue cell types that are directly or indirectly targeted and injured by influenza infection, and follow their recovery under therapy.

